# Evaluation of Hearing Aid Benefit

## 1 Background

In autumn 2020, Phonak released the first iteration of the Paradise line of hearing instruments with Audeo P. In the intervening time, Paradise has been extended to include Naida P, CROS P, and Audeo Life. Beginning in 2022, the Paradise line will be extended once again to include custom devices with Virto P. Performance of this feature set has been tested and validated in other form factors, and relevant claims have been substantiated during those studies, as well. Virto P has been determined to be technically and biologically equivalent to Audeo P; it is, therefore, not necessary to re-validate all functionality and re-substantiate all claims.

Despite the determination that Audeo P clinical data is generally applicable to Virto P, it is nevertheless advisable to collect clinical and usability data with Virto P to demonstrate that our devices provide a clinical benefit to the user relative to no device.

## 2 Objectives

Primary objective:

- To evaluate whether adults with moderate to severe hearing loss (N3/N4) can achieve speech understanding equivalent to their individual dB-opt at a typical conversational input level while using Virto P devices in quiet.

Secondary objectives:

- To evaluate whether Virto P hearing instruments provide improved speech intelligibility in noise compared to the unaided condition in a group of adults with moderate to severe hearing loss (i.e., N3/N4).

## 3 Description of the investigational device

The Virto P is a hearing aid on the Paradise platform and is worn in the ear canal. The microphone(s) pick(s) up sound waves, convert(s) them into an electrical signal which is sent to the Digital Signal Processor (DSP), which is part of the hybrid. The DSP applies the amplification to the electrical signal, which means that the amplitude of the signal gets modified. The modified electrical signal is forwarded to the external receiver, which is held in the ear canal with the aid of an earpiece. The external receiver converts the electrical signal into an acoustic signal and submits it to the ear drum. An integrated Bluetooth antenna enables the hearing aid to also receive digital signals (e.g. streamed music), which will be processed in the same way.

The overall intended purpose of the device is to amplify and transmit sound to the ear and thereby compensate for impaired hearing.

## 4 Design of the clinical investigation

This investigation is a single-center, single-group, open-label clinical investigation. The primary aim of the present investigation is to produce evidence of the clinical benefit of Virto P devices relative to the unaided condition. Because it is unethical to knowingly deprive a group of individuals with a sensory disability (hearing loss) from a well-established treatment (hearing instruments), this trial will rely on laboratory testing in the aided and unaided conditions rather than treatment and control groups to evaluate benefit.

## **5 Risks and benefits of the investigational device and clinical investigation**

Virto P hearing instruments carry only minimal risks under normal use conditions and are intended to give the user auditory access to speech communication. There are no risks associated with the investigation procedures that are not associated with the use of the device. Participants in this investigation will benefit from the ability to hear and communicate in their daily lives, while experiencing only minimal risk associated with the use of the device.

## **6 Endpoints**

Primary objective:

The NU-6 word lists are used extensively in the United States for clinical and research assessments of speech understanding and has been in use for over 50 years (Tillman, Carhart, Wilber, 1963). This test material was selected due to its long history of use in the United States as a measure of monosyllabic word recognition.

Performance on speech recognition tasks varies as a function of hearing loss (Guthrie and Mackersie, 2009). Not all patients will be able to reach 100% correct performance, regardless of the presentation level. Due to this variation, 'excellent' has been defined for this investigation as each individual participant's own maximum performance (PB-max). This investigation will aim to demonstrate equivalency on NU6 word recognition between aided performance at a typical level (65 dB(A)) and the participant's unaided PB-max.

Secondary objective:

The American English Matrix test was selected because it is an externally developed and validated speech test with a steep psychometric function. Because the test estimates an SNR-50, the steep psychometric function makes it a sensitive measure for comparing across multiple conditions. In this case, the test will be administered both with and without hearing aids. These results will be used to support the notion that hearing aids provide a clinical benefit (i.e., hearing speech in noise).

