## **8 Measurements and procedures**

This investigation will evaluate the clinical benefit of the Virto P hearing instruments, and it will generate data to substantiate the claim that Virto P hearing instruments provide the end user with "excellent speech understanding." Virto P hearing instruments are custom, in-the-ear (ITE) devices produced by

Sonova AG under its flagship brand, Phonak. Virto P devices are intended to compensate for mild to profound hearing loss by amplifying speech and other acoustic input to a level that is audible, yet comfortable, for the patient.

One of the most important clinical benefits of any hearing instrument is to provide improved speech intelligibility in difficult listening situations. To evaluate this benefit, participants in this investigation will complete speech-in-noise testing in both an aided and unaided condition. If Virto P is providing the intended benefit, participants should, as a group, perform better in the aided condition than in the unaided condition.

For the purposes of generating data to substantiate the claim that Virto P provides “excellent speech understanding,” ‘excellent’ has been defined as the best possible speech understanding score a user is able to achieve when asked to listen to and repeat words in quiet. This maximum level of understanding will be established for each participant in the unaided condition, and testing will be repeated at a conversational level in the aided condition. Equivalence (defined as +/- 10 %-age points) between these two measures will show that users can understand as much speech as their auditory system will permit when using Virto P and listening to speech at a typical intensity level.

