## **9 Statistical design and analysis**

The sample size for this investigation was determined based on the planned analysis for the primary objective. Sample size calculation was conducted in R using the TOSTER package. The code used to generate the sample size calculation is reproduced below.

```
TOSTER::powerTOSTpaired.raw(alpha = .05,
                           statistical_power = .8,
                           sdif = 12,
                           low_eqbound = -10,
                           high_eqbound = 10)
```

The calculation above assumes an equivalence margin of +/- 10 percentage points and a standard deviation of differences of 12. The power analysis described above yielded a sample size of 13 participants at a power of 0.8 and alpha of 0.05. An additional 3 participants will be recruited to account for potential attrition and/or missing data.

Speech intelligibility data for the primary and secondary objectives from all subjects will be analyzed. A separate analysis will be conducted for the speech intelligibility in quiet measure (primary objective) and the speech intelligibility in noise measure (secondary objective). Participants will not be grouped as a part of these analyses.

The principal investigator will conduct the analysis of the primary endpoint after data has been collected from all participants for all test conditions. This analysis will be conducted in the R statistical computing environment. The analysis will follow a two one-sample t-test procedure to test for equivalency between the aided NU6 performance in quiet and the unaided PB-max performance level. In this procedure, the two one-sample tests will compare the mean difference between the two test conditions to the equivalence margin of 10 percentage points. The two tests will differ only in their alternative hypothesis; one test have an alternative hypothesis that the mean difference is greater than the equivalence margin, the other that the mean difference is less. Rejection of both tests will be interpreted to indicate that the true mean difference is within the equivalence margin above/below zero.

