The principal investigator will conduct the analysis of the secondary endpoint related to speech intelligibility in noise after all data has been collected from all participants in all test conditions. The analysis will be conducted in the R statistical computing environment. The analysis will use a paired t-test to compare the aided speech in noise performance to the unaided speech in noise performance.

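### The order of the aided and unaided Matrix runs is neither specified nor balanced, so under a common order a practice or session effect cannot be separated from device benefit

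*Combined protocol and SAP*

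**What the plan says.** Section 4 describes a single-group, open-label investigation whose primary aim is evidence of benefit relative to the unaided condition. It explains that "this trial will rely on laboratory testing in the aided and unaided conditions rather than treatment and control groups to evaluate benefit". The within-participant comparison therefore stands in for a control group.

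The speech-in-noise comparison appears in three places:

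- Section 6: "the test will be administered both with and without hearing aids". The outcome is an SNR-50.
- Section 8: "participants in this investigation will complete speech-in-noise testing in both an aided and unaided condition".
- Section 9: "The analysis will use a paired t-test to compare the aided speech in noise performance to the unaided speech in noise performance".

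None of these gives the order of the runs, a method of assigning it, a practice list, the allocation of sentence lists, or whether both runs take place at one visit. Section 9 adds that "Participants will not be grouped as a part of these analyses", which leaves no place for order groups in the analysis.

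The only wording about sequence concerns the NU-6 words in quiet. In Section 8 the unaided maximum is established, and then "testing will be repeated at a conversational level in the aided condition".

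**The concern.** In a two-condition within-person comparison, a participant may score differently on the second run for reasons unrelated to the device: familiarity with the test format and sentence material, ease in the booth, or a different day. If everyone follows the same order, that shift enters every paired difference with the same sign. No analysis of those data can then separate it from the device effect.

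The plan as written permits such an order. The devices are custom-made, participation lasts about 2 to 3 weeks, and attendance is by on-site appointment. Unaided testing at an early visit and aided testing after fitting would be a natural way to run the study, although no visit schedule is given.

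Two things are at stake. One is the error rate of the test that carries the benefit aim of Section 4. The other is the estimated benefit in dB, which is shifted by the full order effect even if the device truly helps.

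**Working it through.** **The plan's own figure.** The only stated sample size belongs to the primary equivalence test: margin 10 points, SD of differences 12, alpha 0.05, power 0.8. The normal approximation gives n = (1.645 + 1.282)² × 12² / 10² = 12.33, rounded up to 13, which matches Section 9. With the 3 extra recruits the total is 16. The Matrix test has no stated power, effect size or SD, so I use n = 16 (all complete) and n = 13 (three lost).

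**Model.** Let D be unaided minus aided SNR-50, so that positive values favour the device. Let δ be the true benefit and g the gain on whichever run comes second.

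- Aided second for everyone: E(D) = δ + g
- Aided first for everyone: E(D) = δ − g

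**Assumptions not in the documents.** δ = 0; SD of D is 2 or 3 dB; g is 0.1 to 1.5 dB; two-sided alpha 0.05 (Section 9 states neither alpha nor sidedness for this test).

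**False-benefit rate with aided second.** P = 1 − F(t(0.975, n−1)), where F is the noncentral t distribution function with n−1 degrees of freedom and noncentrality g√n/SD. For n = 16, SD 2 dB and g = 0.5 dB, the noncentrality is 0.5 × 4 / 2 = 1.0, the critical value is 2.131 and P = 15%.

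| Second-run gain (dB) | n = 16, SD 2 | n = 16, SD 3 | n = 13, SD 2 |
|---|---|---|---|
| 0 | 2.5% | 2.5% | 2.5% |
| 0.1 | 3.8% | 3.3% | 3.6% |
| 0.2 | 5.7% | 4.4% | 5.2% |
| 0.5 | 15% | 9% | 13% |
| 1.0 | 46% | 24% | 38% |
| 1.5 | 80% | 46% | 70% |

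**Aided first.** The sign reverses. At n = 16 and SD 2 dB, a gain of 0.5 dB lowers the false-benefit rate to 0.2%, and 1.0 dB lowers it to about 0.01%. The same shift would conceal a real benefit.

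**Balanced order, 8 per order, n = 16 (400,000 simulated trials).** The gain cancels from the mean difference. What remains depends on the analysis:

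- *Plain paired t-test.* The gain stays in the variance. With no true benefit and SD 2 dB, the false-benefit rate falls to 1.5% at a gain of 1.0 dB and 0.3% at 2.0 dB. The test is valid but conservative. At an assumed true benefit of 1.5 dB, power drops from 80% with no order effect to 72% with a gain of 1.0 dB and 62% with 1.5 dB.
- *With an order term.* The false-benefit rate stays near 2.5% and power stays at about 80% throughout.

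**Imbalance after dropout.** If 8 aided-second and 5 aided-first participants complete, the plain mean difference retains (8 − 5)/13 = 23% of the order effect. The average of the two order-group means retains none.

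**The case against.** The strongest reply is that the documents are silent on order and do not prescribe a bad one. That is correct, and it limits the point in several ways.

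- A reader might infer that unaided always comes first. The sequence in Section 8 concerns NU-6 in quiet, a different test serving a different objective. For the Matrix test, the text supports only that order is unspecified.
- A reader might infer that any practice effect counts as benefit. It does so only if aided is second. If aided is first it works against the device, and a mixed order falls between the two.
- A reader might infer that this is the only aided-versus-unaided analysis. The primary analysis also makes such a comparison, to "test for equivalency between the aided NU6 performance in quiet and the unaided PB-max performance level". The Matrix test is the only one that tests superiority over no device.
- A reader might infer that order balance is the only protection available. Practice lists, different sentence lists and same-visit testing also help. The plan mentions none of them.

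The size is also open to challenge. Every gain and SD in the table is assumed. The 46% and 80% figures at n = 16 and SD 2 dB need gains of 0.5 and 0.75 SD, and gains of 0.1 to 0.2 dB give only about 3% to 6%. The endpoint is secondary and is described as supporting evidence.

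All of this stands, but it does not remove the defect. Order is uncontrolled, the study is open-label, and a common order in either direction would leave the estimate uninterpretable by the amount of the order effect.

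**Conclusion.** The concern holds in this form: the plan neither specifies nor balances the order of the Matrix runs, and its analysis has no order term. Under a common order, its only test of benefit over no device estimates the device effect plus or minus the order effect. The direction depends on an order the plan does not state.

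The size cannot be derived from the documents. The calculations show that false-benefit rates well above 2.5% are possible if aided is second and the gain is a material fraction of the SD. They do not show that such gains will occur, nor that the trial will be biased in the device's favour.

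The change should be made before testing begins. The endpoint is secondary, but it carries the benefit aim of Section 4, and a common order cannot be repaired afterwards.

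**What to change.** **Sections 6 and 8.** Randomise each participant to aided-first or unaided-first, 8:8 of the 16. Run both Matrix conditions at the same post-fitting visit, after one unscored practice list, with different sentence lists in the two conditions.

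**Section 9.** Replace the plain paired t-test with an analysis of the paired differences that includes an order term. The benefit estimate is the average of the two order-group mean differences, with the pooled within-group SD and n − 2 degrees of freedom. This keeps the order effect out of both the estimate and the error variance, and it protects against unequal order groups after dropout. State alpha and sidedness, and report the mean difference by order. Amend the sentence that rules out grouping so that it allows the order term.

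**Cost.** A 16-line allocation list, a few extra minutes per participant, and one degree of freedom (15 to 14 with 16 completers). The unaided Matrix run has to wait until the post-fitting visit. The sample size is unaffected, because it was set on the primary endpoint.

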## **7 Inclusion and Exclusion Criteria**

Subjects fulfilling all of the following inclusion criteria are eligible for the investigation:

- N3/N4 sensorineural hearing loss
- Willingness to travel to on-site appointments
- 18-100 years old
- Willingness to use custom hearing instruments
- Fluent in English

The presence of any one of the following exclusion criteria will lead to the exclusion of the subject:

- Cognitive impairment

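### With no unaided NU-6 score planned at 65 dB(A), equivalence to PB-max shows that users reach their maximum while wearing Virto P, but not that the device produced it

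*Combined protocol and SAP*

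**What the plan says.** - **Entry (Section 7).** The hearing criterion is "N3/N4 sensorineural hearing loss", which Section 2 describes as moderate to severe. The other criteria concern age, travel, willingness to use custom devices and fluency in English, and the one exclusion is "Cognitive impairment". None concerns unaided speech scores.
- **Primary comparison (Section 6).** The trial aims to show "equivalency on NU6 word recognition between aided performance at a typical level (65 dB(A)) and the participant's unaided PB-max".
- **Quiet conditions (Section 8).** The maximum is "established for each participant in the unaided condition, and testing will be repeated at a conversational level in the aided condition". No unaided run at 65 dB(A) is named. Equivalence within 10 percentage points either way is read as showing that users understand as much as their auditory system allows when wearing the device.
- **Aim (Section 4).** "The primary aim of the present investigation is to produce evidence of the clinical benefit of Virto P devices relative to the unaided condition".
- **Analysis (Section 9).** Two one-sided tests on the mean paired difference, all subjects analysed, no grouping. Aided and unaided performance are compared only in noise, as the secondary endpoint, by paired t-test.

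**The concern.** An equivalence result supports a claim about the device only if an ineffective device would probably have failed the same test. Here the comparator is the participant's own best unaided score, presumably obtained at whatever level suits that participant. Someone whose unaided score at 65 dB(A) is already close to that maximum gives a difference near zero whether or not the aid does anything. Because no unaided score at 65 dB(A) is planned, the data could not show how far this applied, and the measurement cannot be recovered after the sessions end.

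At stake is how a positive primary result may be worded. Section 4 sets out to show benefit relative to unaided. The secondary comparison does address that, but in noise, with different material (the American English Matrix test) and on a different scale (an SNR for 50% intelligibility). It does not show that word recognition in quiet at 65 dB(A) was deficient without the device.

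**Working it through.** **Inputs (Section 9).** Margin m = 10 points, SD of paired differences 12, alpha 0.05 for each one-sided test, power 0.80, stated n = 13, plus 3 for attrition = 16.

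**Step 1: the plan's own figure.** For a true difference of zero, the normal-approximation formula is n = (z0.95 + z0.90)² × SD² / m² = (1.645 + 1.282)² × 144 / 100 = 12.33, rounded up to 13. The stated sample size reproduces.

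**Step 2: what it takes to pass.** If the observed SD is 12, the mean shortfall from PB-max must be below m − t0.95,n−1 × 12/√n:
- n = 13: 10 − 1.782 × 3.328 = 4.07 points
- n = 16: 10 − 1.753 × 3.000 = 4.74 points

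**Step 3: a device that adds nothing.** The aided shortfall then equals the unaided shortfall at 65 dB(A). The documents do not give that shortfall, so it is an assumption and is shown as a range. Probability that the t-based equivalence test passes, with normal differences and SD 12:

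| Mean unaided shortfall (points) | n = 13 | n = 16 |
|---|---|---|
| 0 | 0.76 | 0.88 |
| 2 | 0.69 | 0.80 |
| 4 | 0.51 | 0.60 |
| 6 | 0.30 | 0.35 |
| 8 | 0.14 | 0.16 |
| 10 | 0.05 | 0.05 |
| 15 | 0.001 | 0.001 |

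**Step 4: mixed groups, device adds nothing.** Suppose k of 13 participants have no unaided shortfall at 65 dB(A) and the rest share the one shown (SD 12 within participant, simulated):

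| Shortfall of the others | k = 8 | k = 10 | k = 12 |
|---|---|---|---|
| 10 points | 0.47 | 0.62 | 0.73 |
| 20 points | 0.07 | 0.29 | 0.64 |
| 30 points | 0.001 | 0.06 | 0.50 |

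The test is on the group mean, so participants with no deficit must be very numerous, or the others' deficits small, before an inert device is likely to pass.

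**Step 5: a device that works partly.** Suppose it closes half of a 20-point deficit, leaving 20 × 0.5 = 10 points, exactly the margin. At n = 16 it passes with probability 0.05 if nobody is near PB-max unaided, 0.17 if 4 of 16 are, and 0.42 if 8 of 16 are. At n = 13 with 8 near PB-max it is 0.47.

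**Step 6: can the planned sample support the missing comparison?** Take a two-sided paired t-test of aided against unaided NU-6 at 65 dB(A), alpha 0.05, assuming SD 12 carries over. The noncentrality is gain / (12/√n). For a 10-point gain this is 10/3.328 = 3.00 at n = 13 and 10/3.000 = 3.33 at n = 16, giving power of 0.79 and 0.88. For a 15-point gain, power is at least 0.98 at both sizes.

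**The case against.** The strongest reply is that the primary test answers the question put to it. Sections 2 and 8 ask whether users can reach their maximum at a conversational level while wearing the device. That is a question of attainment, and Section 8 treats benefit separately, through the comparison in noise. This stands: the equivalence test is valid for the attainment claim.

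A reader might go further and infer that participants already near PB-max can carry an ineffective device to a pass. The documents do not support that as a general statement. They give no unaided scores at 65 dB(A), and they describe the sample as having moderate to severe loss. At a mean shortfall equal to the margin an inert device passes 5% of the time. With 8 of 13 near PB-max and the rest 20 points short it passes 7% of the time.

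A reader might also infer that the eligibility list is at fault and should require a deficit. The gap lies in the missing test condition. Selecting on one word-list score would be noisy, would conflict with Section 9's rule that all subjects are analysed, and would shrink an analysis sized at 13. Nor is it practical to demand proof that the shortfall exceeds 10 points: for a true shortfall of 15 points at SD 12, a one-sided test at 0.05 has power of about 0.41 at n = 13 and 0.48 at n = 16.

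Finally, the documents do not list the levels used to find PB-max, so 65 dB(A) might happen to be among them. Even so, no such score is named as a condition or used in any analysis.

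**Conclusion.** The point holds in a limited form. The primary test can show that users reach their maximum with Virto P. It cannot by itself show that the device brought them there, and no other planned measurement does so in quiet, although Section 4 names benefit relative to unaided as the primary aim.

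How much this matters depends on a quantity that the documents do not report. At SD 12 and n = 16, the chance that an inert device passes falls from 0.80 at a mean shortfall of 2 points to 0.05 at 10. The risk is material only if the mean shortfall is well below the margin, or if the device works partly and many participants have little deficit. These figures assume normal differences, the plan's SD of 12, and shortfalls chosen here for illustration. This is a cheap improvement to what the trial can conclude, and the primary test itself needs no correction.

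**What to change.** - **Sections 6 and 8:** add one unaided NU-6 list at 65 dB(A), under the same presentation conditions as the aided test.
- **Section 9:** keep all subjects in the primary equivalence test. Beside it, report the mean unaided shortfall from PB-max at 65 dB(A) with its confidence interval. Add a supportive paired comparison of aided and unaided NU-6 at 65 dB(A) in quiet.
- **Interpretation:** attribute equivalence in quiet to the device only if that comparison shows a gain. Otherwise report attainment alone.
- **Leave unchanged:** eligibility, the primary analysis set and the sample size.

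The cost is one extra word list per participant and a little more analysis. If the true gain is well under 10 points the supportive comparison may be inconclusive at this sample size, and the report should then say so.
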